9.1 Primary Efficacy Endpoint

The primary efficacy endpoint in Phase II is the BOR as determined by RECIST v1.1.

9.1.1 Objective Response Rate

The primary summary measure of Best Overall Response (BOR) is the ORR, defined as the proportion of patients with a best overall response of CR or PR based on local investigator

assessment, as defined in RECIST v.1.1. The denominator in the calculation of the ORR will be the number of patients with measurable disease at baseline in the FAS / PPS as appropriate. All these patients included in the denominator will be categorized by their BOR (CR, PR, SD, PD, NE).

Confirmation of response is required for declaring PR or CR in the ORR. A confirmed response is defined as a CR or PR followed by a CR or PR at least 4 weeks later (allowing a window, this will need to be at least 3.5 weeks after the original assessment). Patients who have a PD event (progression or death) immediately after 2 or more consecutive missed/non-evaluable tumor assessment visits, will have a BOR of NE. Specifically for patients who die with no evaluable follow-up tumor assessments or no evaluable baseline assessment, if the death occurs immediately after the first 2 scheduled scans, then the BOR will also be NE. An exception to this rule is if the patient (with no evaluable follow-up tumor assessments or no evaluable baseline assessment) dies within 2 visits of first dose of study drug, then the BOR will be PD (for death in the absence of progression).

Tumor response will be determined per local investigator's assessment, according to RECIST v.1.1

Individual lesion measurements and overall response assessments will be listed by patient and assessment date. Best overall response per RECIST v.1.1 will be listed and tabulated. Change in tumor size for individual patients will be shown in spider plots. Duration of Treatment, Tumor Response and Response Duration will be shown in swimmer plots. Best overall change in tumor size for individual patients will be shown in waterfall plots and may be repeated at 13 and 26 weeks (Cycle 3 and Cycle 6).

Best overall response analysis per RECIST v.1.1 will be repeated for PPS. BOR will be summarized for overall and by Synovial cohort.

ORR and DCR (CR + PR + stable disease [SD]) will be summarized with accompanying 95% Clopper-Pearson's confidence interval. A patient is eligible for an assessment of stable disease only after 16 weeks from day of first dose. Any SD assessed before 16 weeks will not be counted as SD in the DCR.

DoR and time-to-response for patients who experience a CR or PR at any time on study will be listed by patient. Duration of response is the time in months from the date of first documented objective response until the date of progression or death (whichever occurs first). If a large proportion of patients achieves a response (e.g. 5/10), Kaplan-Meier plots for DoR will also be produced, and the median DoR will be estimated. The time-to-response is defined as the time from first dose to their first CR or PR.

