9.5.2 Phase II: Efficacy

In Phase II, the primary endpoint is the best overall response (BOR). The primary summary measure is ORR, defined as the proportion of patients with a BOR of complete response (CR) or partial response (PR) based on local Investigator assessment, as defined in RECIST v.1.1. ORR will be analyzed separately for the Phase II cohorts. Confirmation of response is required for declaring a PR or CR as the BOR. A confirmed response is defined as a CR or PR followed by a CR or PR at least 4 weeks later. ORR will be summarized with accompanying 95% confidence interval.

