9.9.2 Phase II Expansion Cohorts

A Simon two-stage design will be used for each Phase II cohort using a 10% probability of a Type 1 error, a 20% probability of a Type 2 error, and assuming a target response rate of 20% versus 5% response rate for available treatment options. If there are no responses among the first 9 patients in a cohort, then accrual in that cohort will stop. If there is at least one response, at the discretion of the Sponsor up to an additional 15 patients may be accrued for a total of up to 24 patients (with at least 3 responses to support further evaluation).

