4.1 Sample Size

Dose decisions will be guided by the BLRM. Among the simulations that were conducted, the mean sample size was 27 patients, and the sample size was less than 33 patients in over 80% of simulations.

A Simon two-stage design will be used for each Phase II cohort using a 10% probability of a Type 1 error, a 20% probability of a Type 2 error, and assuming a target response rate of 20% versus 5% response rate for available treatment options. If there are no responses among the first 9 patients in a cohort, then accrual in that cohort will stop. If there is at least one response, at the discretion of the sponsor up to an additional 15 patients may be accrued for a total of up to 24 patients (with at least 3 responses to support further evaluation).

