10.3 Pharmacodynamics

Cytokines and lymphocytes are analyzed and are covered by this SAP. No other pharmacodynamics analysis would be performed.

11 Interim Analysis

No formal interim analysis is planned during Phase I. The BLRM will be updated after each dose-escalation cohort and the MTD / RP2D will be determined at the end of Phase I (see Section 3.1).

A formal interim analysis will be conducted during Phase II. ORR will be evaluated for the first 9 patients in each Phase II cohort to determine whether enrollment may continue (see Section 4.1).

12 Changes in the Planned Analysis

There were no substantial changes from the planned analyses described in the protocol version 4.0, dated 24 Feb 2020 to those presented in this SAP. The following minor detail has changed from the protocol:

- All Patients Set has been added to allow for additional disposition summaries to be conducted
- Safety RP2D Analysis Set has been added to allow for some analyses to be conducted on patients pooled across phases if they receive RP2D.

13 References

14 Appendices

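### SAP 9.1.1 accepts confirmation of response from 3.5 weeks where protocol 9.5.2 requires at least 4, and SAP Section 12 does not declare the change (minor)

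*SAP*

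**What the plan says.** Protocol 9.5.2 makes confirmation part of the Phase II primary endpoint: "Confirmation of response is required for declaring a PR or CR as the BOR". It then fixes the interval: "A confirmed response is defined as a CR or PR followed by a CR or PR at least 4 weeks later". No tolerance is given there.

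SAP 9.1.1 repeats the 4-week definition and adds a parenthesis that lowers it: "allowing a window, this will need to be at least 3.5 weeks after the original assessment".

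SAP Section 12, which is meant to record departures from the protocol, opens with "There were no substantial changes from the planned analyses described in the protocol version 4.0". It lists only two added analysis sets; the confirmation window is not among them.

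The decision rules rest on this count. SAP 4.1 (and protocol 9.9.2) says: "If there are no responses among the first 9 patients in a cohort, then accrual in that cohort will stop". With at least one response the sponsor may extend the cohort to 24, and three responses are needed to support further evaluation. Protocol 9.8 and SAP Section 11 base the look at the first 9 patients on ORR, which both documents define on confirmed responses.

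**The concern.** Two governing documents give different limits for the same primary endpoint, and the difference is not declared. A CR or PR repeated after 25, 26 or 27 days is a confirmed response under the SAP and an unconfirmed one under the protocol.

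The SAP rule accepts everything that the protocol rule accepts and somewhat more, so any discrepancy can only raise the response count. The counts are small: one patient separates stopping from continuing at the interim, and one patient separates 2 from 3 of 24. Responses are read by local investigators in an open-label study, with central review only optional (protocol 7.4.3). SAP Section 9 plans no sensitivity analysis that would show the ORR under the strict rule, so a reader of the report could not tell whether the looser limit had mattered.

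**Working it through.** **1. The stated design reproduces.** Error rates from protocol 9.9.2: "using a 10% probability of a Type 1 error, a 20% probability of a Type 2 error". The same section sets the null rate at 5% and the target at 20%. Rule: 9 patients in stage 1, stop at 0 responses; otherwise 15 more, with success at 3 or more of 24.

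P(success | p) = sum over x = 1 to 9 of P(Bin(9, p) = x) × P(Bin(15, p) ≥ 3 − x), where the second factor is 1 for x ≥ 3.

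| | p = 0.05 | p = 0.20 |
|---|---|---|
| Stop at 0 of 9 | 0.95^9 = 0.630 | 0.80^9 = 0.134 |
| x = 1 | 0.2985 × 0.1709 = 0.0510 | 0.3020 × 0.8329 = 0.2515 |
| x = 2 | 0.0629 × 0.5367 = 0.0337 | 0.3020 × 0.9648 = 0.2914 |
| x ≥ 3 | 0.0084 | 0.2618 |
| P(success) | 0.0931 | 0.8047 |

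Type I error is 9.3% and power 80.5%, within the stated 10% and 80%. These figures depend on the response rates and the decision rule, not on how confirmation is timed.

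**2. The range in dispute.** Protocol: 4 × 7 = 28 days. SAP: 3.5 × 7 = 24.5 days. In whole days the rules disagree only for gaps of 25, 26 and 27 days.

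**3. Can scheduled scans fall in that range?** Scans are every 8 weeks to week 40 and every 12 weeks after that (protocol Tables 7-2 and 7-3). Their timing is counted from C1D1 and does not shift with dosing delays (protocol 7.2). Visit windows are ±7 days on treatment (7.2) and ±14 days in follow-up (7.3). The smallest gap is the scheduled interval less both windows.

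| Pair of consecutive scans | Smallest gap |
|---|---|
| Every 8 weeks, both on treatment | 56 − 7 − 7 = 42 days |
| Every 8 weeks, treatment to follow-up | 56 − 7 − 14 = 35 days |
| Every 8 weeks, both in follow-up | 56 − 14 − 14 = 28 days |
| Every 12 weeks, both on treatment | 84 − 14 = 70 days |
| Every 12 weeks, both in follow-up | 84 − 28 = 56 days |

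No pair falls on days 25 to 27. Both rules classify every pair of on-schedule scans alike, so the tolerance rescues no on-schedule responder.

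**4. What has to happen for the rules to differ.**

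- A repeat scan is taken off schedule and lands 25 to 27 days after the first CR or PR.
- No later scan, at least 28 days after the first, shows CR or PR by the data cut. If one does, the protocol rule confirms the response too.
- For a decision to change, the count must also sit on a boundary: otherwise 0 of 9 at the interim, or otherwise 2 of 24 at the end.

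Example: two responses confirmed at 8 weeks, plus one first seen at a scheduled scan, repeated on day 26 and progressed at the next scan. The SAP counts 3 of 24 and the protocol 2 of 24.

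The second condition is easiest to meet at the first-9 interim, where a later confirming scan may not yet exist.

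**The case against.** The strongest reply is that the tolerance is close to inert. No scheduled pair of scans is affected, no 4-week confirmatory scan is planned, and the Amendment 2 change table (protocol 13.5.2) records that scans beyond the main schedule are not required to confirm response. A durable response repeated early would normally be confirmed by a later scheduled scan under either rule. All of this stands, and it is why the point is minor.

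It is also fair that the decision rules are softer than a formal test. Only the stop at 0 of 9 is firm; stage 2 opens at the sponsor's discretion, three responses merely support further work, and SAP Section 4 rules out formal hypothesis tests.

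A reader might infer that the looser rule pushes type I error above the stated 10%. The same formula gives 11.5% if the null response rate became 5.5%, and 13.9% at 6%. But 0.5/5.5 is about 1 in 11, and 1/6 is 1 in 6, of all counted responders who would have to owe their status to the window alone. Nothing in the documents supports such a frequency, and with scans on schedule the increase is zero.

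What the reply does not answer is that the texts disagree on the primary endpoint, the change is undeclared, and the documents do not forbid off-schedule scans.

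**Conclusion.** The inconsistency is real: at least 4 weeks in the protocol, at least 3.5 weeks in the SAP, for the same Phase II primary endpoint, and not declared in SAP Section 12. Its reach is narrow. It affects only an off-schedule repeat scan at 25 to 27 days with no later confirming scan by the data cut. Such a case is likely rare; the documents give no frequency. Where it occurs it favours the drug, and it could turn 0 into 1 of 9 or 2 into 3 of 24.

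A reader might infer from the texts alone that responses rejected by the protocol will open stage 2 or meet the 3-of-24 rule. The scan schedule does not support that, because on-schedule scans are classified identically. The design figures (9.3% and 80.5%) stand, and no figure for inflated type I error can be drawn from the documents.

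This rests on reading the general visit windows as applying to scan dates, and on intervals being counted in whole days. Severity: minor.

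**What to change.** Delete the 3.5-week parenthesis from SAP 9.1.1, so that the protocol's 28-day minimum governs both the first-9 interim and the final ORR. Add that a response repeated only at 25 to 27 days stays unconfirmed until a later scan, at least 28 days after the first, shows CR or PR.

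If the sponsor prefers to keep the window, amend the definition in protocol 9.5.2, list the change in SAP Section 12, and report the interim and final counts under the strict 4-week rule alongside.

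The first option costs SAP wording only. No on-schedule responder is lost. A patient repeated early waits for the next scheduled scan, which is on the 8-week cycle up to week 40 and the 12-week cycle after that. Either option should be in place before the first Phase II interim count.

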ECOG performance status	X											X					D1 of each cycle	
Hematology panel	X	X	X	X	X	X	X	X	X	X	X		X				D1 of each cycle	
Chemistry panel	X		X		X	X	X	X	X	X	X		X				D1 of each cycle	
Thyroid function	X						X				X							
Urine pregnancy test (women of childbearing potential)	X						X				X						D1 of each cycle	
PK and Immunogenicity																		
Pharmacokinetic sampling	8x	3x	8x	X	4x	4x	2x		2x		2x		2x			2x on D1 of odd-numbered cycles		
Immunogenicity sampling	X		X		X		X				X						D1 of odd-numbered cycles	
Disease Assessment																		
CT/MRI scans and disease assessment												X				Q8W to W40 (C3, C5, C7, C9, C11), then Q12W (C14, C17, etc)		
Tumor biopsy	Between C1D9 and C1D16 (required for ≥ 10 patients in Phase II, optional for all other patients) Optional for all patients at time of progression																	

IMCnyeso administration	X		X		X	X	X	X	X	X	X	X	X	X	D1, D8, D15, and D22 of each cycle
-------------------------	---	--	---	--	---	---	---	---	---	---	---	---	---	---	------------------------------------

AE = adverse event; C#D# = Cycle # Day #; [REDACTED]; CT = computerized tomography; ECG = electrocardiogram; ECOG = Eastern Cooperative Oncology Group; EOI = end of infusion; hr = hour(s); min = minutes; MRI = magnetic resonance imaging; [REDACTED]; PK = pharmacokinetics; Q#W = every # weeks; [REDACTED]; W = week.

ECG assessments are to be done pre-dose and within 1 hour of EOI on indicated days.

Vital signs (body temperature, pulse, respiratory rate, and blood pressure; in addition, oxygen saturation should be collected for \geq first 3 cycles of treatment) are to be assessed at the following timepoints:

- C1D1/C1D2 and C1D8/C1D9: pre-dose (within 2 hours), EOI (within 15 min), every 2 hours (\pm 15 min) through 12-hour post-EOI, every 4 hours (\pm 30 min) until discharge
- All other doses: pre-dose (within 2 hours), EOI (within 15 min), and 1-hour post-EOI (\pm 15 min)

Pharmacokinetics samples are to be collected at the following timepoints:

- C1D1 and C1D8: pre-dose (within 2 hours), EOI (within 15 min), 1-hour post-EOI (\pm 15 min), 2-hour post-EOI (\pm 15 min), 4-hour post-EOI (\pm 15 min), 6-hour post-EOI (\pm 30 min), 8-hour post-EOI (\pm 1 hr), and 12-hour post-EOI (\pm 3 hr)
- C1D2: 24-hour post-EOI (\pm 4 hr), 36-hour post-EOI (optional, \pm 4 hr), and 48-hour post-EOI (optional, \pm 4 hr)
- C1D9: 24-hour post-EOI (\pm 4 hr)

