8.6 Dose Interruptions and Reductions

The number of IMCnyeso dose interruptions, dose reductions, escalations and re-escalations will be summarized. A dose is considered interrupted when it is not administered for any reason during a visit (i.e. investigator answers the question in eCRF: "If No, reason for dose interruption"), when a visit is delayed by ≥ 7 days or omitted, or if an infusion is started and then stopped part-way through. If the dose is administered, but the investigator states it is reduced compared to last visit or if there is a reduction compared to the planned dose (for example, if a patient is assigned to 30/100/300 and receives 30 mcg on C1D8 that is a reduction from the planned dose of 100 mcg.), then the dose is considered as reduced (i.e. the investigator' answers the question in eCRF: "If Yes, reason for dose reduction").

Reasons for dose interruptions and dose reductions will be listed by patient and summarized.

9 Efficacy Analysis

Analysis of efficacy endpoints will be performed using the FAS and PPS for Phase II and only on FAS for Phase I.

No sensitivity or exploratory analysis are planned.

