9.2 Secondary Efficacy Endpoints

9.2.1 Progression-free Survival

PFS is defined as the time from first dose until the date of objective progression, or death from any cause, whichever occurs first. Patients who progressed or died immediately after two or more missed scheduled tumor assessments will be censored at date of last adequate assessment with evidence of no progression. Patients who have not progressed or died at the time of analysis will be censored at the time of the latest date of assessment from their last evaluable RECIST 1.1 assessment. These censoring rules apply regardless of what concomitant medications may have been taken or if the patient discontinued treatment prior to their last assessment. A sensitivity

analysis may be performed if subjects without objective disease progression receive a new anti-cancer therapy potentially affecting their results. In this analysis such patients will then be censored at the date of the last adequate response assessment prior to the new anti-cancer therapy.

$PFS \text{ (months)} = (\text{Event date} - \text{date of first dose} + 1) / 30.4375$

The PFS will be presented graphically using Kaplan-Meier plots including all patients treated at the MTD or RP2D and by overall and Synovial cohort. Median PFS time and the proportion of patients who are progression-free at 3, 6, 9 and 12 months will be estimated for each group. To note, the 95% confidence interval will be calculated using “conftype = loglog” option within the Proc Lifetest procedure in SAS software.

PFS per RECIST v.1.1 will be listed by patient and tabulated.

PFS per RECIST v.1.1 will be repeated for the PPS for Phase II.

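### The SAP's missed-visit rule sets BOR to NE even when a CR or PR was already confirmed, so a confirmed responder can be counted as a non-responder in the primary ORR

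*SAP*

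**What the plan says.** In Phase II the primary summary measure is ORR, the proportion of patients whose BOR is CR or PR by local assessment. Protocol Section 9.5.2 requires confirmation: "A confirmed response is defined as a CR or PR followed by a CR or PR at least 4 weeks later". It has no rule about missed visits.

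SAP Section 9.1.1 repeats the confirmation requirement, with a 3.5-week lower window, and then adds that patients with a PD event (progression or death) "immediately after 2 or more consecutive missed/non-evaluable tumor assessment visits, will have a BOR of NE". The next two sentences concern patients with no evaluable follow-up or baseline scan. A death right after the first two scheduled scans is also NE, and a death within two visits of first dose is PD. No other exception is given.

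NE counts against the response rate. Of patients with measurable disease at baseline, the SAP says: "All these patients included in the denominator will be categorized by their BOR (CR, PR, SD, PD, NE").

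Two nearby rules bear on the same patients. For PFS (SAP Section 9.2.1), a patient who progresses or dies after two or more missed assessments "will be censored at date of last adequate assessment with evidence of no progression". For duration of response, SAP Section 9.1.1 says: "DoR and time-to-response for patients who experience a CR or PR at any time on study will be listed by patient".

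SAP Section 4.1 sets the cohort rule: stop if there are no responses in the first 9; otherwise enroll up to 24, "with at least 3 responses to support further evaluation".

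**The concern.** A gap in imaging followed by progression makes the date of progression uncertain. That is a good reason to censor PFS, and to avoid a BOR of PD when nothing else was observed. It does not undo a response that two scans had already established. As written, the NE rule looks only at what happened around the progression event, so it overrides the confirmed response.

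The tabulated ORR would then be too low. With at most 24 patients per cohort and a threshold of three responses, one patient can decide whether the criterion is met. The per-protocol repeat uses the same derivation, so it would carry the same error. SAP Section 9 states: "No sensitivity or exploratory analysis are planned". The response and DoR listings and the swimmer, spider and waterfall plots would let a careful reader find such a patient, but would not correct the table.

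**Working it through.** **1. Does the wording reach confirmed responders?**

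Scans are "Q8W to W40 (C3, C5, C7, C9, C11), then Q12W" (Protocol Table 7-2). Take this patient:

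| Week | Result |
|---|---|
| 8 | PR |
| 16 | PR |
| 24 | missed |
| 32 | missed |
| 40 | PD |

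- Protocol Section 9.5.2: the second PR comes 8 weeks after the first, and 8 ≥ 4, so the response is confirmed and BOR is PR.
- SAP Section 9.1.1, NE sentence: two consecutive missed visits come immediately before PD, so BOR is NE.
- SAP early-death exception: the patient has evaluable follow-up scans, so it does not apply.
- ORR: the patient is in the denominator and not in the numerator.
- PFS: the patient is censored at week 16, and the earlier scans are kept.
- DoR: the patient is listed.

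The general sentence cannot be read as covering only patients without evaluable scans. The SAP treats that subset in the sentence that follows and says those patients are NE as well.

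**2. The plan's own design figures**

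Inputs from SAP Section 4.1: p0 = 0.05, p1 = 0.20, type I error 10%, type II error 20%, n1 = 9, stop at 0/9, N = 24, success at 3 or more.

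P(success | p) = P(X1 = 1)·P(X2 ≥ 2) + P(X1 = 2)·P(X2 ≥ 1) + P(X1 ≥ 3), with X1 ~ Bin(9, p) and X2 ~ Bin(15, p).

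- p = 0.20: 0.3020 × 0.8329 + 0.3020 × 0.9648 + 0.2618 = 0.8047
- p = 0.05: 0.2985 × 0.1710 + 0.0629 × 0.5367 + 0.0084 = 0.0931

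Both meet the stated 80% power and 10% type I error, so the design reproduces.

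**3. Effect of one recoded patient (Clopper-Pearson 95%)**

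| Count | ORR | 95% CI | At least 3? |
|---|---|---|---|
| 3/24 | 12.5% | 2.7% to 32.4% | yes |
| 2/24 | 8.3% | 1.0% to 27.0% | no |

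**4. How often a cohort sits on the threshold at 20% ORR**

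P(exactly 3 in total, stage 1 passed) = P(Bin(24, 0.2) = 3) − P(Bin(9, 0.2) = 0)·P(Bin(15, 0.2) = 3) = 0.1493 − 0.1342 × 0.2501 = 0.1158.

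This is the share of cohorts in which one recoding would change the result. It is not the probability that the result changes.

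**5. Illustration with an assumed share q of responders recoded**

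The documents give no value for q.

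- *Final count only.* Stage 1 is judged on the true responses. The final number of responders n is then thinned to Bin(n, 1 − q), and three or more must remain.
- *Both stages.* The response rate is 0.20(1 − q) throughout.

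| q | Final count only | Both stages |
|---|---|---|
| 0% | 80.5% | 80.5% |
| 5% | 78.6% | 77.7% |
| 10% | 76.3% | 74.5% |

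The first column is the more cautious. A recoding at the 9-patient look needs the gap and the progression to have happened by then, which is less likely.

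**The case against.** The best counter-argument is context. ORR is defined by reference to RECIST v1.1, the SAP reports no substantial change from the protocol (Section 12), and footnote b to Protocol Table 13-4 keeps a confirmed PR through later assessments. On that view the NE block only says when a late event is too remote to be scored PD. That may be what the authors meant. But the footnote attaches to the stable-disease row and says nothing about missed visits, and a general statement in Section 12 does not override an explicit derivation rule. A programmer would follow the rule as written.

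Several other points stand, at least in part:

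- **DoR comparison.** The DoR listing does not require confirmation, so an unconfirmed responder could already have a listed DoR without a BOR of CR or PR. The mismatch with DoR is weak evidence on its own.
- **PFS comparison.** Censoring has no direct equivalent for BOR. The PFS rule shows a different treatment of the same pattern, not a contradiction.
- **Rarity.** The pattern needs a confirmed response, two consecutive missed or non-evaluable scans, and then an event. On-treatment imaging is mandatory (Protocol Table 7-4), and scan dates do not move with dosing delays (Protocol Section 7.2). It may never happen.
- **Limited consequence.** The SAP plans no formal hypothesis test, and expansion is at the sponsor's discretion.

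These points bear on how much the problem matters. They do not change what the sentence says.

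**Conclusion.** The concern holds. Applied as written, SAP Section 9.1.1 can reclassify a response confirmed under Protocol Section 9.5.2 as NE and count it as a non-response in the primary Phase II measure. The error runs one way: it can hide activity but cannot create a false positive. Its weight comes from small cohorts and a low threshold, where one patient separates 3/24 from 2/24. The loss of 1.9 points (80.5% to 78.6%) or 4.2 points (80.5% to 76.3%) in the chance of meeting the criterion is an illustration. It rests on assumed recoding shares of 5% and 10%, recoding at the final count only, and a true ORR of 20%. If no patient follows the pattern, or the program already protects confirmed responses, the effect is zero. It should be fixed because the written rule gives a wrong primary-endpoint result for a definable patient and is simple to correct.

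**What to change.** Keep the sentence in SAP Section 9.1.1 and add after it:

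> This rule applies only to patients with no CR or PR confirmed before the missed visits; a CR or PR confirmed before the gap is retained as BOR.

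Agree this before Phase II results are known, so that it is not decided around an individual responder. The cost is one SAP clause and one condition in the BOR derivation program. No new data and no protocol amendment are needed, because the protocol already defines a confirmed response.

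The clause does not settle a related question. The same sentence also turns stable disease at or beyond 16 weeks into NE, which lowers DCR. The team should say whether that is intended.

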7.2 Treatment Period Schedule

The treatment period starts with Day 1 of Cycle 1 (C1D1). A treatment cycle is defined as 28 days for the purposes of scheduling procedures and evaluations.

Any assessments required on C1D1 that are also performed as part of Screening do not need to be repeated on C1D1 if the data were obtained 72 hours prior to the first dose of study treatment. For subsequent visits, pregnancy testing may be performed up to 72 hours prior to dosing and other safety assessments may be performed up to 24 hours prior to dosing.

During the study visits, all tests and/or procedures should occur on schedule whenever possible. A visit window of ± 7 days (with a minimum of 7 days between doses of IMCnyeso) is allowed unless otherwise indicated in the protocol. If study drug infusions are delayed, the assessments associated with those infusions should be rescheduled accordingly. However, the timing of protocol-specified radiological assessments should be calculated in weeks using C1D1 as reference and should not be adjusted because of delays in treatment.

Assessments required during the treatment period are presented by visit in [Table 7-2](#). For patients receiving IPE, follow the alternate Cycle 1 schedule provided in [Section 13.4](#). Assessments marked “X” should be performed prior to dosing. Assessments that are to be performed at multiple timepoints are marked with the number of timepoints (including optional timepoints, if applicable) for the visit (eg, 2 \times is twice) and details of the timepoints are provided in the footnote. Additional details regarding the assessments are provided in [Section 7.4](#). Please refer to [Section 6](#) for dosing details. Patients will continue treatment until they meet criteria for discontinuation, as described in [Section 6.16](#).

Table 7-2: Schedule of Treatment Period Assessments

Procedure	Cycle 1						Cycle 2				Cycle 3				Later Cycles			
Day of Cycle	1	2	8	9	15	22	1	8	15	22	1	8	15	22	Visits on Days 1, 8, 15, and 22			
Adverse events	X	X	X	X	X	X	X	X	X	X	X	X	X	X		X		
Concomitant medications	X	X	X	X	X	X	X	X	X	X	X	X	X	X		X		
Safety Assessments																		
Complete physical examination	X																	
Abbreviated physical examination			X		X	X	X	X	X	X	X	X	X	X		D1 of each cycle		
Weight	X						X				X						D1 of each cycle	
Vital signs	~14x	~14x		3x	3x	3x	3x	3x	3x	3x	3x	3x	3x	3x		3x each dosing day		
12-lead ECG (single)	2x						2x				2x					2x on C4D1, C5D1, and C6D1		

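### Stable disease counts toward the DCR only from week 16, with no tolerance, although the second scan is due on that day and may be done earlier

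*SAP*

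**What the plan says.** SAP 9.1.1 defines the DCR as complete response plus partial response plus stable disease (SD), with a Clopper-Pearson 95% interval. Two sentences set the time condition for SD. The first reads "A patient is eligible for an assessment of stable disease only after 16 weeks from day of first dose". The second reads "Any SD assessed before 16 weeks will not be counted as SD in the DCR". Neither gives a tolerance.

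The same section does relax another interval. Confirmation of response nominally needs 4 weeks between scans, but with a window "this will need to be at least 3.5 weeks after the original assessment".

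Protocol Table 7-2 schedules scans "Q8W to W40 (C3, C5, C7, C9, C11), then Q12W (C14, C17, etc". Protocol 7.2 adds three rules:

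- Cycle length: "A treatment cycle is defined as 28 days for the purposes of scheduling procedures and evaluations".
- Visit window: plus or minus "7 days (with a minimum of 7 days between doses of IMCnyeso) is allowed unless otherwise indicated in the protocol".
- Scan timing: "radiological assessments should be calculated in weeks using C1D1 as reference and should not be adjusted because of delays in treatment".

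No separate window for scans is stated. Protocol 7.3 widens the visit window to plus or minus 14 days in follow-up, which includes patients who stop treatment without progression and continue to be scanned.

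**The concern.** The cut-off coincides with the due date of the second scan, and the protocol permits that scan to be early. Take two patients with the same course: SD at the second scan and progression at the week-24 scan. If the second scan is on day 108, the patient is not counted as controlled; if it is on day 113, the patient is. Both scans comply with the protocol.

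The error can only lower the DCR, and it depends on how sites book scans. The SAP plans no sensitivity analysis of the DCR that would reveal it. The two SD sentences also leave day 112 itself undecided, so two programmers could implement different rules.

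**Working it through.** **1. The cut-off and the scan date.** Cycle 5 Day 1 falls (5 − 1) × 28 = 112 days after Cycle 1 Day 1, and 112 / 7 = 16.0 weeks. As a check on the mapping, Cycle 11 Day 1 is 10 × 28 = 280 days = 40 weeks, which agrees with Table 7-2. The second scan is nominally due on the cut-off.

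**2. Permitted dates for the second scan**, counting days after first dose:

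| Setting | Window | Permitted days | Dates | Before day 112 | On or before day 112 | Before day 105 |
|---|---|---|---|---|---|---|
| On treatment | ±7 days | 105–119 | 15 | 7 (47%) | 8 (53%) | 0 |
| Follow-up | ±14 days | 98–126 | 29 | 14 (48%) | 15 (52%) | 7 (24%) |

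These are shares of permitted dates, not predicted shares of patients.

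**3. The boundary day.** Read literally, the eligibility sentence requires more than 112 days, so a scan on the nominal date fails. The exclusion sentence rejects only scans earlier than 112 days, so the same scan passes. SAP Section 4 adds a further ambiguity by defining study day as date minus Cycle 1 Day 1 date plus 1. Elapsed day 112 is then study day 113, and elapsed day 111 is study day 112.

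**4. Who is affected.** A patient is lost from the DCR only if all of these hold: the second scan is early, it shows SD, there is no confirmed response, and no SD is documented at week 24 or later. A patient with SD again at week 24 still counts.

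**5. Size.** One patient in a full Phase II cohort of 24 is 1/24 = 4.2 points. As an illustration with assumed counts, 8/24 = 33% (95% CI 16% to 55%) becomes 6/24 = 25% (10% to 47%) if two patients are lost.

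The documents give neither the share of patients whose second scan is their only chance to qualify (q) nor the share of those scans that are early (e). Both are assumed here, with expected loss = q × e:

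- q = 5%, e = 10%: 0.05 × 0.10 = 0.5 points, or 0.12 of 24 patients.
- q = 10%, e = 25%: 0.10 × 0.25 = 2.5 points, or 0.6 patients.
- q = 30%, e = 7/15: 0.30 × 0.467 = 14 points, or 3.4 patients.

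**6. Does a lower limit admit the week-8 scan?** Its latest permitted day is 56 + 7 = 63 on treatment, or 56 + 14 = 70 in follow-up. Both are well below 98 and 105, so the requirement for SD beyond the first scan is kept.

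**The case against.** **The window may not apply to scans.** The ±7 days is a general visit window, and imaging is treated separately in the sentences that follow. With weekly dosing and at least 7 days between doses, the Cycle 5 Day 1 dose cannot precede day 112 in an uninterrupted course. This shows that dosing visits drift late. It does not bind scans, which are timed from Cycle 1 Day 1 independently of dosing and for which no narrower window is given. What stands is that nothing supports an even spread of scans around day 112.

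**A fixed minimum duration is a legitimate definition.** SD on day 107 followed by progression at week 24 does not document SD at 16 weeks. That is fair, and the confirmation tolerance concerns a different interval, so it does not by itself require one here. But a limit placed exactly on a scheduled scan separates patients by booking rather than by course of disease.

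**Little depends on the DCR.** This stands. It is not an endpoint in Protocol Table 4-1 or SAP 3.2, and the two-stage rule counts responses. SAP 9.1.1 also lists every response assessment by date.

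**A stronger reading is tempting.** From the 7 of 15 dates, a reader might infer that about half of patients with SD at the second scan lose disease control, or might settle on a single large figure for the loss. The documents do not support this: they give no distribution of scan dates and no SD counts, and patients with later SD or a confirmed response are unaffected.

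**Conclusion.** The point holds as a minor but real defect in a descriptive summary. The SD rule has no tolerance at a limit that coincides with a scheduled scan, so some protocol-compliant SD is discarded and the DCR is biased downward by scan timing. The two SD sentences also conflict on day 112.

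The size is 4.2 points per affected patient in a cohort of 24. The number affected is unknown, and the 0.5 to 14 point range rests entirely on the assumed values of q and e. The conclusion also assumes that the general visit window applies to scans, as it does by default when no other window is given.

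A reader might infer that the primary Phase II result is at risk. It is not: the ORR uses only confirmed responses, and SD plays no part in the two-stage decision.

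**What to change.** Replace the two SD sentences in SAP 9.1.1 with one rule: SD counts toward the DCR if documented at or after 16 weeks less the permitted assessment window.

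- **Limit.** For on-treatment scans this is at least 112 − 7 = 105 days from first dose. If scans in follow-up are also to be covered, it is 112 − 14 = 98 days.
- **Boundary.** State that the boundary day is included.
- **Counting.** State whether the limit is in elapsed days or in study day, which is one higher.
- **Display.** Say how patients whose only SD is earlier than the limit appear in the best overall response table, since the eligibility sentence leaves this unclear.

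The cost is a short SAP edit and a slightly less strict duration requirement for SD. The study is open-label and the SAP already tabulates enrolled cohorts, so the change should be made and dated before the DCR is analysed; afterwards it could look data-driven.
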